
Exclusion:

Age < 18

Conversion to open surgery

Acute cholecystitis

Prior common bile duct surgery

Presence of diastasis recti or umbilical hernia

4. Surgical Technique

Standard LC using:

10 mm umbilical camera port

10 mm epigastric port

Two 5 mm subcostal ports

Fascial closure was performed only at the umbilical site using polyglactin sutures.

Epigastric port sites were not sutured.

Gallbladder retrieval performed using a bag.

5. Postoperative Management & Follow-Up

Pain Control:

IV paracetamol and tramadol postoperatively. VAS recorded at 6 and 24 hours.

Discharge & Follow-up:

Routine discharge on Day 1 if no complications. All patients followed for 12 months.

Hernia Diagnosis:

Symptomatic patients evaluated with ultrasonography. Asymptomatic patients underwent

scheduled USG at 6 and 12 months.

6. Statistical Analysis

- Data analyzed with SPSS v26 and RStudio.
- Categorical data were analyzed using Fisher's exact or Chi-square tests
- Continuous variables were compared using Student's t-test or Mann–Whitney U test
- Univariate and multivariate logistic regression performed to evaluate TSH risk factors.
- Significance threshold: P < 0.05

7. Results Summary

Demographics:

Age, BMI, and other baseline factors were comparable between groups.

Outcomes:

- Hernia rate: 6 in Group U, 5 in Group E (all at umbilicus)
- Retrieval time shorter in Group E (P = 0.013)
- Pain lower in Group U at 6h (P = 0.027)
- No difference in 24h VAS scores
- Multivariate Analysis:
- Fascial widening was the only independent predictor of TSH (OR = 4.08, P = 0.05)

8. Discussion

- All trocar site hernias (TSH) occurred at the umbilical site, regardless of extraction route.
- This confirms the umbilicus as the most vulnerable location for hernia development after
- laparoscopic cholecystectomy.
- Epigastric extraction avoided direct stress on the umbilical site and was associated with no
- hernias at the epigastric port.
- Gallbladder retrieval was faster via the epigastric route, offering operative efficiency.
- Early postoperative pain (6h) was slightly higher with epigastric extraction but not clinically
- limiting.
- Fascial widening during extraction was the only independent risk factor for TSH.
- These findings support preferential use of the epigastric port for specimen retrieval to
- minimize hernia risk.

9. Conclusion

While trocar site selection did not statistically alter the incidence of hernia, all hernias occurred at

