the umbilicus, highlighting its vulnerability. Fascial widening during extraction was a key

modifiable risk factor. Epigastric retrieval may offer operative efficiency, but at a slight cost in

postoperative discomfort.

10. Ethical Considerations

- Approved by the Clinical Research Ethics Committee of Istanbul University of Health
- Sciences, Umraniye Training and Research Hospital.
- All participants provided written informed consent.
- Study conducted in accordance with the Declaration of Helsinki.
- No funding received. No conflicts of interest declared.

STATISTICAL ANALYSIS PLAN (SAP)

Study Title: Umbilical Trocar Site Is the Usual Suspect for Trocar Site Hernia After

Laparoscopic Cholecystectomy: A Prospective Study

Version: 1.0

Prepared by: [name]

Study Sponsor: Umraniye Research and Training Hospital

Principal Investigator: Ass. [name]. [name]

1. Study Overview

This is a prospective, randomized, controlled clinical trial evaluating the incidence of trocar site hernia (TSH) in patients undergoing laparoscopic cholecystectomy, comparing gallbladder extraction via the umbilical versus epigastric port.

2. Study Objectives

Primary Objective:

To assess whether the site of gallbladder retrieval (umbilical vs. epigastric trocar) affects the incidence of trocar site hernia.

Secondary Objectives:

To compare postoperative pain levels at 6 and 24 hours between groups

To assess gallbladder retrieval time

To identify independent risk factors for the development of trocar site hernia

3. Endpoints

Primary Endpoint:

Incidence of trocar site hernia (clinical or ultrasonographic diagnosis within 12 months)

Secondary Endpoints:

- Gallbladder retrieval time (in seconds)
- Visual Analogue Scale (VAS) pain scores at 6 and 24 hours postoperatively
- Occurrence of fascial widening and its association with TSH

• Logistic regression model identifying independent risk factors for TSH

4. Analysis Populations

Intention-to-Treat (ITT):

All randomized patients, excluding those who converted to open surgery or were lost to follow-

up.

Per Protocol (PP):

Patients who completed surgery and 12-month follow-up without major protocol deviations.

5. General Statistical Methods

- Statistical significance threshold set at P < 0.05 (two-sided).
- All statistical analyses will be performed using SPSS v26.0 and RStudio v4.2.0.
- Results will be reported with appropriate confidence intervals (CIs) and effect sizes when
- applicable.

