6. Data Handling and Assumptions

Missing Data:

No imputation will be performed.

Patients lost to follow-up will be excluded from analysis of outcomes they did not complete.

Outliers:

Checked visually (boxplots, scatterplots).

No exclusions unless clinically justified.

Normality Testing:

Shapiro-Wilk test used for continuous variables.

7. Baseline and Demographic Comparisons

Descriptive statistics: mean ± SD for normally distributed data; median (min-max) for non-

normal data; frequency (%) for categorical variables.

Comparisons:

• Categorical variables: Chi-square or Fisher's exact test

• Continuous variables: Student's t-test or Mann–Whitney U test depending on distribution

8. Primary Endpoint Analysis

Incidence of TSH:

Compared between the umbilical and epigastric groups using Fisher's exact test.

9. Secondary Endpoint Analyses

- Gallbladder retrieval time: Compared using Mann–Whitney U test (non-normal distribution
- anticipated).
- Postoperative pain scores (VAS at 6h and 24h): Assessed separately at both time points.
- Compared using Mann–Whitney U test.
- Exploratory regression analyses: Univariate logistic regression to identify factors associated
- with TSH Variables with P < 0.2 or known clinical relevance will be entered into a
- multivariate logistic regression model.
- Odds Ratios (OR), 95% CI, and P-values will be reported.

10. Subgroup Analyses

Subgroup analysis will be performed for patients in the umbilical extraction group to evaluate the

impact of fascial widening on TSH incidence using logistic regression.

11. Software

All analyses will be conducted using:

- SPSS v26.0 (IBM Corp., Armonk, NY, USA)
- RStudio v4.2.0 (The R Foundation)

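### The planned analyses do not match the port widened to the hernia site or compare the widening–hernia association by arm, so they support an association, not a modifiable cause

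*Combined protocol and SAP*

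**What the plan says.** SAP 3 lists "Occurrence of fascial widening and its association with TSH" as a secondary endpoint, with no restriction to one arm.

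SAP 9 plans "Exploratory regression analyses: Univariate logistic regression to identify factors associated" with TSH, followed by a multivariate model. The entry rule is "Variables with P < 0.2 or known clinical relevance will be entered into a" multivariate logistic regression. The candidate variables are not listed, and no arm is excluded.

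SAP 10 says "Subgroup analysis will be performed for patients in the umbilical extraction group to evaluate the" and continues "impact of fascial widening on TSH incidence using logistic regression". It names no covariates, no matching analysis in Group E and no arm-by-widening term.

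CSR 7 gives the counts and the site: "Hernia rate: 6 in Group U, 5 in Group E (all at umbilicus". It reports OR 4.08, P = 0.05 for widening from the multivariate analysis, without a CI. CSR 8 states "Fascial widening during extraction was the only independent risk factor for TSH" and says that epigastric extraction spared the umbilicus direct stress. CSR 9 then presents widening as an important risk factor that can be modified.

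No section defines widening, says at which port it was recorded, or gives its frequency by arm.

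**The concern.** Widening was not randomised. It may damage the port, or it may mark a patient or gallbladder trait (weak fascia, a large stone) that leads to hernia anyway. Calling it modifiable asserts the first.

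The trial's structure bears on this question. If widening happens during extraction, then in Group E it happens at the epigastric port, yet all 5 Group E hernias were at the umbilicus. An association between epigastric widening and umbilical hernia in Group E could not be mechanical and would point to a marker. The SAP 9 model, which does not code the port, could count a widened epigastric port as exposure for an umbilical hernia. SAP 10, confined to Group U, cannot show whether the association differs by arm. What is at stake is a headline conclusion of the report: whether surgeons are told that avoiding widening prevents hernia.

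**Working it through.** **Inputs from the documents.** Group U 6/50 and Group E 5/50 with TSH, P = 1.00 (CSR 1); all hernias umbilical (CSR 7); OR 4.08, P = 0.05 (CSR 7); two-sided 0.05 (SAP 5). Widening prevalence is not given, so 10% to 50% is assumed.

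**1. The stated figure.** Fisher's exact test on 6/50 against 5/50 gives P = 1.00 (OR 1.23). It reproduces.

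**2. Share of hernias at an extraction port.** Only Group U hernias qualify: 6/11 = 55%. The other 5/11 = 45% were at a port not used for extraction.

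**3. Precision of the reported OR.** SE = ln(4.08)/1.96 = 1.406/1.96 = 0.72. The 95% CI is exp(1.406 ± 1.96 × 0.717), about 1.00 to 16.6. If P was rounded from between 0.045 and 0.055, the lower limit lies between 0.97 and 1.03.

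**4. What a pooled 4.08 would mean if widening acted only in Group U.** This step treats 4.08 as if it were an unadjusted pooled OR. Solve the pooled 2×2 table (100 patients, 11 hernias) for the number of widened hernias, subtract the Group E share expected under no association (5 × prevalence), and compute the Group U OR from what is left. Example with 30% widened in both arms: 6.53 widened hernias pooled; less 5 × 0.3 = 1.5 leaves 5.03 of Group U's 6; OR = (5.03 × 34.03)/(0.97 × 9.97) = 17.7.

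| Widened in U | Group U OR needed, same prevalence in E | Group U OR needed, none widened in E |
|---|---|---|
| 20% | 12.5 | 4.8 |
| 30% | 17.7 | 6.1 |
| 40% | 38.3 | 9.5 |

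At 50% in both arms it cannot be reached: 6.08 widened hernias would be needed from 6. In reverse, a Group U OR of 4.08 with no association in Group E pools to 2.25, 2.17, 2.09 and 2.02 at 20%, 30%, 40% and 50% widened in both arms.

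**5. What a by-arm comparison could show.** Woolf SE of a log OR = √(1/a + 1/b + 1/c + 1/d), using expected cells. The SE of the difference is √(SE_U² + SE_E²), and power is about Φ(ln 4.08/SE_diff − 1.96), taking OR 4.08 in U and 1 in E. At 30% widened: SE_U = 0.90, SE_E = 1.03, SE_diff = 1.37, power = Φ(1.03 − 1.96) = 18%.

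| Widened | Group E 95% CI if its OR is 1 | Power for an arm difference |
|---|---|---|
| 10% | 0.05 to 21.8 | 11% |
| 20% | 0.10 to 10.1 | 15% |
| 30% | 0.13 to 7.5 | 18% |
| 40% | 0.15 to 6.6 | 18% |
| 50% | 0.16 to 6.4 | 17% |

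Every Group E interval includes 4.08. The ratio of ORs needed for 80% power is about 44 or more. Exact Fisher power for an OR of 4.08 over the same prevalence range is about 15% to 33% in Group U alone, 10% to 29% in Group E, and 37% to 53% in all 100 patients.

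**The case against.** The defence has four good points.

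- **Group E is not left out.** A reader of SAP 10 alone might infer that the plan ignores widening in the epigastric arm. It does not: SAP 3 and SAP 9 cover all patients, and SAP 9 can adjust for measured traits. What remains is that neither matches port to hernia site nor compares arms, and 11 events with unlisted covariates leave little room for adjustment. Confining SAP 10 to the arm where the extraction port is also the hernia site is defensible for a mechanical question; it just does not separate cause from marker.
- **Group E may not be usable as a negative control.** It is tempting to assume that the data for this check exist. The documents do not show that widening was recorded in Group E, or at which port. The epigastric site was not sutured, so nothing shows that its fascia was assessed. If umbilical widening was recorded in both arms, Group E is not a negative control.
- **A null result in Group E would not prove causation.** Weakness local to the umbilical fascia could produce both umbilical widening and hernia, yet leave no trace at the epigastric port. With 6 and 5 events, a rule that labels widening cause or marker from the arm contrast would be unreliable.
- **Step 4 is not evidence about this trial.** A reader might conclude from 12.5 to 38.3 that the reported OR is implausible. Those figures rest on equal prevalence by arm, and the reported OR is adjusted. With no widening in Group E the range drops to 4.8 to 9.5.

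All four stand as limits on the point. None supplies the missing port definition or justifies the causal wording in CSR 9.

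**Conclusion.** The concern holds as a gap in definition and analysis, and as an over-reading in the conclusion. The analyses in SAP 9 and SAP 10 cannot tell damage to the port from a trait that goes with widening. For 5 of the 11 hernias, extraction widening at the epigastric port is excluded as a mechanical cause. An OR of 4.08 whose implied CI starts at about 1.00, for a non-randomised exposure with no stated port, supports an association only.

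The site argument rests on CSR 7 and CSR 8 as written: all hernias umbilical, widening during extraction. Steps 4 and 5 rest on the assumed prevalence and illustrate how much the missing breakdown matters; they are not re-analyses. The documents do not support the stronger conclusion that widening is merely a marker. The point concerns a secondary endpoint and leaves the randomised comparison untouched.

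**What to change.** 1. Define fascial widening, and record or state the port at which it was assessed.
2. In SAP 9, use widening at the umbilical port as the exposure for umbilical hernia, and keep randomised arm in the model.
3. In SAP 10, tabulate widening (by port) against umbilical hernia in each arm, with exact ORs and 95% CIs, labelled as a descriptive check.
4. State the reading in advance: a similar association with epigastric widening in Group E argues for a marker; its absence does not establish causation.
5. Reword CSR 9, and any text drawn from it, to report an association. Give the CI for the OR.
6. If the port was not recorded in Group E, say so and limit the conclusion to an association.

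Cost: SAP wording, plus one more 2×2 table if the data were recorded. The by-arm estimates will be very imprecise, and the all-patient OR may become less favourable once exposure is restricted to the umbilical port.
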